**Pelvis RCT: Impact of Surgery on Pain in Lateral Compression Type Pelvic Fractures**

**NCT: 02625766**

**December 28, 2020**

### Statistical Analysis

[figure not shown]
The primary analyses were based on the intent-to-treat principle. The primary analysis for pain and secondary analysis for functional outcome estimated the difference in the average treatment effect based on a longitudinal assessment within the initial 12-weeks after the fracture. This approach uses each patient's multiple outcome assessments to compare the average pain and function experienced over the 12-week period between the treatment groups. For these analyses, we used a Bayesian hierarchical model that applied a prior probability of no treatment difference based on the conflicting evidence in the prior literature [3-6]. This is akin to an initial assumption that there is "no difference" in pain or functional outcome between the treatment groups. In addition to estimating the average treatment effect, we calculated the posterior probability (meaning conditioning the prior distribution on the data at hand) of treatment benefit with operative treatment under various minimally clinical important difference (MCID) thresholds. The models included a dummy variable for each patient as a random intercept, an autoregressive correlation structure, and adjusted for whether the treatment was randomly assigned, the patient's pre-injury narcotic use, and a time-varying covariate that measured narcotic use at each time point. Multivariable linear regression was used to analyze the treatment effect on hospital length of stay and time to mobilization. Outcome data were missing in 16% of the sample at 2-weeks, and 14% of the sample at 6-weeks and 12-weeks, and was therefore imputed using multiple imputation for the final models [16]. To assess possible effect measure modification based on the initial degree of displacement, we stratified the sample to create two subgroups, patients with  $\geq 5$ mm of displacement and patients with  $< 5$ mm of displacement. We then calculated the average effect of operative treatment on pain in each of the subgroups. In addition, we compared the average treatment effect of operative fixation on pain with posterior-only fixation compared to operative fixation with anterior and posterior fixation. Additional sensitivity analyses recalculated the pain and function outcomes to separately compare the treatment effects between patients enrolled in the randomized cohort and the observational cohort. The analyses were performed using R Version 3.6.1 (Vienna, Austria) with the packages *lme4*, *rstan*, *brms*, and *mice*.

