
We took two critical steps to understand the potential for biased treatment estimates from pooling the results from the randomized and non-randomized participants. First, we performed sensitivity analyses to separately examine the results for the randomized and non-randomized cohorts. These analyses suggested similar (or even larger) estimated treatment benefits from surgery within the RCT data. Second, we included willingness to be randomized as a potentially confounding variable in our final analysis models, despite there being no evidence that it affected treatment.

[figure not shown]
The ability to assess the probability of different magnitudes of treatment benefit is a unique characteristic of Bayesian data analysis, and is not possible with traditional non-Bayesian statistical hypothesis testing. Despite this inherent difference in statistical principles, it should be noted that the average treatment benefits reported from our Bayesian analysis are nearly identical to the results obtained using traditional multilevel linear regression models (results not reported).

Additional results from the described analyses, that were not included in the main article, are provided below.

[figure not shown]
**Posterior probability of reduced pain.** Posterior probability of reduced pain with operative treatment within 12 weeks of injury.

[figure not shown]
**Mean pain stratified between randomized and nonrandomized patients.** The mean Brief Pain Inventory scores and 95% credible intervals within the initial 12-weeks of injury for minimally displaced complete lateral compression pelvis fracture patients. The patients are stratified based on their study type (randomized trial versus observation) and treatment type (operative versus nonoperative treatment). The pain scores are adjusted for the study type, prior narcotic use, and narcotic use at each time point.

**Posterior probability of improved function.** Posterior probability of improved function, measured with the Majeed score, with operative treatment within 12 weeks of injury.

**Mean function stratified between randomized and nonrandomized patients.** The mean Majeed scores and 95% credible intervals within the initial 12-weeks of injury for minimally displaced complete lateral compression pelvis fracture patients. The patients are stratified based on their study type (randomized trial versus observation) and treatment type (operative versus nonoperative treatment).

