**Posterior probability of reduced pain, stratified by initial posterior pelvic ring fracture displacement:** The posterior probability of surgical fixation achieving a clinically significant reduction in mean BPI pain scores stratified by fracture displacement (<5mm versus  $\geq$ 5mm). Several possible clinically significant pain reduction thresholds are presented.

	Displacement $\geq$ 5mm	Displacement < 5mm	Difference in Probability
Mean Difference in Pain	2.2 (95% CrI: 0.9 - 3.5)	0.9 (95% CrI: 0.1 - 1.8)	
> 0	> 99%	98%	2%
> 0.5	99%	82%	17%
> 1.0	97%	41%	56%
> 1.5	88%	8%	80%
> 2.0	65%	1%	64%

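### The SAP sets out to assess effect modification by displacement but gives no estimate, with uncertainty, of the difference between the two subgroup effects; subtracting threshold probabilities does not supply one.

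*SAP*

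**What the plan says.** The aim is stated in the SAP, Statistical Analysis: "To assess possible effect measure modification based on the initial degree of displacement, we stratified the sample to create two subgroups". The method is the next sentence: "We then calculated the average effect of operative treatment on pain in each of the subgroups". No contrast of the two effects is described. The models "adjusted for whether the treatment was randomly assigned, the patient's pre-injury narcotic use, and a time-varying covariate that measured narcotic use at each time point", together with a patient random intercept and an autoregressive correlation structure. No treatment-by-displacement term is listed.

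The SAP's closing table, on pain by initial displacement, is captioned "The posterior probability of surgical fixation achieving a clinically significant reduction in mean BPI pain scores stratified by fracture displacement". It prints a mean difference and 95% credible interval for each subgroup, then each subgroup's probability that the benefit exceeds 0, 0.5, 1.0, 1.5 and 2.0 points. The final column, "Difference in Probability", reads 2%, 17%, 56%, 80% and 64%. The SAP introduces this material as supplementary: "Additional results from the described analyses, that were not included in the main article, are provided below".

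**The concern.** Effect modification is the difference between the two subgroup effects, and that difference has its own uncertainty. Two separate effects with separate intervals do not give it. The reader can subtract 0.9 from 2.2, but must reconstruct the interval under assumptions about shape and correlation that the SAP does not supply.

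The only between-subgroup quantity offered is a difference of tail probabilities. It depends on where the threshold falls relative to the two posteriors and on how precise each posterior is. An entry of 80% beside a stated aim of assessing effect modification could be taken as strong evidence of it, or even as a probability of it. It is neither. Whether surgery relieves pain more in displaced fractures is the SAP's own question, and the described analysis does not answer it with uncertainty.

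**Working it through.** **Inputs** (SAP, displacement table): effect at 5 mm or more 2.2 (0.9 to 3.5); effect below 5 mm 0.9 (0.1 to 1.8); the five pairs of threshold probabilities. Assumptions: near-normal posteriors, and zero correlation between them because the subgroups hold different patients. Both are varied below.

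**1. Reproduce the column.** 99 - 82 = 17; 97 - 41 = 56; 88 - 8 = 80; 65 - 1 = 64. The first entry, 2, follows if the value printed as above 99% is taken as about 100%. The column is plain subtraction.

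**2. Posterior SDs from interval widths.** (3.5 - 0.9)/3.92 = 0.663 and (1.8 - 0.1)/3.92 = 0.434.

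**3. Check the approximation, and test the column with no modification.** The last column below sets both effects to the precision-weighted mean, (2.2/0.663² + 0.9/0.434²)/(1/0.663² + 1/0.434²) = 1.29, and keeps the two SDs.

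| Threshold | ≥5 mm: printed / normal (%) | <5 mm: printed / normal (%) | Column: printed / normal (points) | Column if effects were equal (points) |
|---|---|---|---|---|
| >0 | >99 / 99.95 | 98 / 98.1 | 2 / 1.9 | -2.4 |
| >0.5 | 99 / 99.5 | 82 / 82.2 | 17 / 17.3 | -8.2 |
| >1.0 | 97 / 96.5 | 41 / 40.9 | 56 / 55.6 | -7.9 |
| >1.5 | 88 / 85.4 | 8 / 8.3 | 80 / 77.1 | +6.1 |
| >2.0 | 65 / 61.9 | 1 / 0.6 | 64 / 61.3 | +9.1 |

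The approximation matches the printed subgroup probabilities to within about 3 points. With the posteriors held fixed, the column would fall to about 11 points at a threshold of 3 and 0.3 at 4. With equal effects it is still not zero.

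**4. The direct contrast.** Difference = 2.2 - 0.9 = 1.3. SD = √(0.663² + 0.434²) = 0.792. 95% interval = 1.3 ± 1.96 × 0.792 = -0.25 to 2.85. P(>0) = Φ(1.3/0.792) = Φ(1.64) = 0.95. P(>0.5) is about 0.84 and P(>1.0) about 0.65.

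**5. Sensitivity.**
- Combining the asymmetric printed limits (MOVER) instead of SDs: -0.28 to 2.83.
- Fitting normals to the tabulated probabilities (>99% taken as 99.5%): means 2.25 and 0.90, SDs 0.648 and 0.434; difference 1.35, SD 0.780, interval -0.18 to 2.88, P(>0) 0.96.
- Rounding of the printed figures, zero correlation: lower limit -0.42 to -0.08, P(>0) 0.93 to 0.97.
- Correlation from -0.2 to 0.4, printed figures: lower limit -0.39 to +0.06, P(>0) 0.93 to 0.98.
- Rounding and correlation (0 to 0.3) together: lower limit -0.42 to +0.13, P(>0) 0.93 to 0.99.

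**The case against.** The best reply is that the table makes no false claim. The column is accurately labelled, follows the SAP's approach of probabilities across MCID thresholds, and is nowhere called an estimate of effect modification. Both effects and intervals stand beside it. Unequal precision alone would produce only small entries of mixed sign, whereas the printed ones are all positive and mostly far larger, and the probability of a positive difference is about 0.95. So the direction the table suggests survives. The empty cell in the mean-difference row is what the column heading implies and proves nothing. The main article is not among the documents and some SAP figures are not shown, so a contrast could have been reported elsewhere.

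Most of this stands as a limit on the point. The table's direction is not misleading, and the finding concerns only the SAP's text and table. The gap remains: the stated aim is effect modification, and the described method ends at within-subgroup effects. An accurate label does not turn a difference of tail probabilities into an answer to that question.

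A second objection concerns cost. Outcomes were multiply imputed, and the imputation model is not described. If it left out the treatment-by-displacement relation, the contrast could be pulled toward zero, and existing draws would carry that over. This is fair and is reflected in the fix.

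**Conclusion.** The concern holds for the SAP as written. That no contrast is specified or printed there is clear from the text. The reconstructed size is less certain: about 1.3 BPI points, 95% interval -0.25 to 2.85, probability about 0.95 of exceeding zero, resting on near-normal, independent posteriors and rounded inputs. A larger benefit in the more displaced group is fairly well supported, but its size is imprecise. Zero lies just inside the interval under independence and can fall just outside it under modest positive correlation, so neither presence nor absence of modification should be asserted from these figures. The exact answer needs the posterior draws. The matter is worth correcting but confined to one supplementary subgroup analysis; the primary pain estimate does not depend on it.

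**What to change.** Fit one model with a treatment-by-displacement interaction, or contrast the posterior draws of the two subgroup effects within each imputed dataset and then pool. Report the posterior mean, 95% credible interval and probability above zero for the difference in effects in place of the present column. If thresholds are wanted, report the probability that the difference in effects exceeds each one. Label the analysis exploratory. State whether the imputation model allowed the treatment effect to vary with displacement; if it did not, re-impute before computing the contrast.

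The cost is one model term or one contrast, and one table column, plus a rerun of the imputation if needed. No new data are required. The evidence for effect modification will look weaker than the current column suggests.

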Table II. Clinical grade based on a score out of 100 points for working and 80 points for non-working patients (see text)

Working before injury	Not working before injury	Grade
> 85	> 70	Excellent
70 to 84	55 to 69	Good
55 to 69	45 to 54	Fair
< 55	< 45	Poor

STUDY POPULATION

The study population will be patients aged 18-80 with a lateral compression type pelvic fracture that go on to receive operative or non-operative treatment of the injury.

Inclusion Criteria:

1. Patients that have one of the following pelvic fractures (includes bilateral sacral fractures): lateral compression type 1, lateral compression type 2, lateral compression type 3.
2. Patients between 18 and 80 years of age, inclusive.
3. Patient has reached skeletal maturity.
4. The patient's pelvic fracture is a result of trauma (includes polytraumatized patients).
5. The patient/family/guardian is English-speaking.
6. The patient's surgeon agrees to randomization (the patient is amendable to either operative or non-operative treatment).
7. Patient enrollment and, if applicable, patient randomization, can occur within 96 hours post injury.

Exclusion Criteria:

Patients who satisfy any of the following exclusion criteria will be ineligible for enrollment in the study:

1. The patient has prior surgical hardware in place that precludes intervention.
2. If the patient's pelvic fracture is classified as LC1 and the associated sacral fracture is incomplete as indicated by failure to violate both the anterior and posterior cortex.
3. The patient received prior surgical intervention for his/her current pelvic injury.
4. The patient has sacral morphology that precludes percutaneous fixation.
5. The patient is non-ambulatory due to an associated spinal cord injury.
6. The patient was non-ambulatory pre-injury.
7. The patient is currently pregnant.
8. The patient is enrolled in another study that does not allow co-enrollment.
9. The patient is likely to have severe problems maintaining follow up.

ADJUDICATING ELIGIBILITY

To ensure consistency in the application of inclusion criteria and in the classification of injuries, all fractures will be re-evaluated by a surgeon in Shock Trauma who is not treating the patient. These evaluations will be based on slides of AP and lateral x-rays. Each case will be independently reviewed. The non-treating surgeon will convene to discuss the case if there is disagreement regarding eligibility or classification of the injury to resolve differences of opinion.

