Patients enrolled in the operative treatment group will undergo surgical intervention for their pelvic fracture. The surgeon will decide the best surgical technique as per standard of care for the patient's injury. The patient will mobilize as per the surgeon's instructions and x-rays will be taken at follow-up clinic appointments to determine if the injury is healing properly. If additional surgery is required or other complications arise, this will be recorded within the study follow-up forms.

CLINICAL EVALUATION

A summary of the clinical evaluations is outlined below and can also be found in Appendix B.

Medical Record Review

During the index hospitalization, information about the participant (medical history, height and weight, etc.) and the participant's injuries and hospital stay will be collected, including mechanism, presence of and severity of other orthopaedic and non-orthopaedic injuries, procedures done in the hospital, overall (and ICU) length of stay, time to mobilization (bed to chair) in physical therapy, pain medication administration, and discharge disposition.

Assessment of Study Injuries

The extent and severity of the pelvic injury will be prospectively assessed by the treating surgeon after initial x-rays are taken. The following injury characteristics will be collected:

- Lateral compression type classification of the pelvic fracture
- Skin defect associated with the pelvic injury
- Muscle and tendon injury associated with the pelvic injury
- Deep vein injury associated with the pelvic injury
- Nerve injury associated with the pelvic injury

Assessment of Study Injury Treatment

For participants undergoing operative treatment, the following information will be obtained:

- Type of fracture stabilization
- Type and timing of fixation revisions
- Limb Complications (type, severity, treatment)

Assessments at 2 weeks, 6 weeks, 3 months, and 1 year post injury

- Complications since last follow-up (type, severity, treatment)
- Assessment of fracture healing
- Weight bearing status and ambulation
- Use of ambulatory devices
- Pain assessment
- Narcotic use assessment

X-rays

AP and lateral x-rays at admission, post-operative treatment (when applicable), and at the 2 week, 6 week, 3 month and 1 year follow-ups will be obtained. These x-rays are obtained per standard of care.

PARTICIPANT INTERVIEWS

A summary of the participant interviews performed are outlined below and can also be found in Appendix D.

Baseline Hospital Interview

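### The 5 mm displacement subgroups rest on a measurement whose reader, image, timing and concealment are not stated, and the protocol did not plan the split

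*SAP*

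**What the plan says.** The SAP (Statistical Analysis) sets out the subgroup step as follows: "To assess possible effect measure modification based on the initial degree of displacement, we stratified the sample to create two subgroups". The subgroups are 5 mm or more and less than 5 mm. The closing table is headed as "stratified by initial posterior pelvic ring fracture displacement" and gives, for operative treatment:

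- 5 mm or more: mean pain difference 2.2, 95% credible interval 0.9 to 3.5.
- Under 5 mm: mean pain difference 0.9, 95% credible interval 0.1 to 1.8.
- Probability of a benefit above 1.0 point: 97% v 41%.

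The protocol (Clinical Evaluation, Assessment of Study Injuries) has the treating surgeon assess the extent and severity of the injury prospectively, once the initial films are available. It then introduces a list with "The following injury characteristics will be collected". The list has five items: "Lateral compression type classification of the pelvic fracture", and skin, muscle or tendon, deep vein and nerve injury. Displacement is not one of them.

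There is also a second reader. Under Adjudicating Eligibility, "all fractures will be re-evaluated by a surgeon in Shock Trauma who is not treating the patient", working from AP and lateral films. Under Study Schedule, Screening and Consent, a non-treating surgeon further adjudicates the study injury characteristics after consent. Appendix B has a single general row for study injury characteristics, in the post-randomisation baseline column. The X-rays paragraph provides for films at admission, after any operation, and at each follow-up visit.

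**The concern.** A baseline subgroup analysis is sound only if membership is settled independently of treatment and outcome. Three features of this trial make that more than a formality.

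- Treatment is surgery or no surgery, and neither document describes blinding. The treating surgeon knows the treatment, and post-operative films can reveal it.
- The SAP pools randomised and observational patients. For the observational patients, randomisation does not protect the comparison within a subgroup.
- A continuous measurement is cut at a single value. For fractures near 5 mm, a small difference in reading changes the subgroup.

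At stake is the statement about which patients gain more from surgery. The overall pain estimate does not depend on the split.

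**Working it through.** **Step 1. Trace the variable through the documents.**

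| Question | What the supplied text gives |
|---|---|
| Is displacement a listed item? | No (Assessment of Study Injuries). The wording on extent and severity could cover it loosely. |
| Who reads it? | Two surgeons have roles in assessing injury characteristics, but neither is named as reader of displacement. |
| From which image? | The SAP says *initial*. That fixes the state described, not the film used or the date it was read. |
| With treatment and outcome concealed? | Not stated. |
| Is a displacement subgroup planned? | Not in the protocol's objectives or Data Analysis, and displacement is not a stratification factor under Randomization. |
| Could a form field exist? | Yes. The forms are an attachment that was not supplied (Appendix D). |

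**Step 2. Check that the SAP's table agrees with its own intervals.** Treat each posterior as roughly normal, with SD = (upper limit - lower limit) / 3.92.

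- 5 mm or more: (3.5 - 0.9) / 3.92 = 0.663
- Under 5 mm: (1.8 - 0.1) / 3.92 = 0.434

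Then P(benefit > t) = 1 - Φ((t - mean) / SD):

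| Threshold t | 5 mm or more: SAP | 5 mm or more: recomputed | Under 5 mm: SAP | Under 5 mm: recomputed |
|---|---|---|---|---|
| 0 | >99% | >99.9% | 98% | 98.1% |
| 0.5 | 99% | 99.5% | 82% | 82.2% |
| 1.0 | 97% | 96.5% | 41% | 40.9% |
| 1.5 | 88% | 85.4% | 8% | 8.3% |
| 2.0 | 65% | 61.8% | 1% | 0.6% |

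The lower subgroup matches. The upper one is within about 3 percentage points, which rounded inputs or a non-normal posterior would explain. The table is coherent, so the approximation can be used for the next step.

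**Step 3. Compute the contrast that the SAP does not report.** The last column of the SAP table subtracts one subgroup's probability from the other's at each threshold. That is not an estimate of how far the two effects differ. The direct contrast is:

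- Difference: 2.2 - 0.9 = 1.3 points
- SD: √(0.663² + 0.434²) = 0.792
- Approximate 95% interval: 1.3 ± 1.96 × 0.792 = -0.25 to 2.85
- P(difference > 0) = Φ(1.3 / 0.792) = about 95%

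Each mean is rounded to 0.1, so the difference could be anywhere from 1.2 to 1.4. The probability then runs from 93.5% to 96.1%. Independence of the two posteriors is an assumption.

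**The case against.** The best defence is that the protocol arranges more than its five-item list suggests. Injury extent is assessed prospectively after the initial films. A non-treating surgeon adjudicates study injury characteristics after consent, and the SAP twice calls the displacement initial. The post-randomisation column of Appendix B also holds demographics, height and weight, and mechanism of injury. It therefore shows when a form is completed, not that an admission film was read after allocation. A displacement field may well be on a form we cannot see. The analysis is also supplementary, and it is offered as an examination of possible effect modification.

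Most of this stands, and it rules out two stronger readings that a reader might infer.

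- *That displacement had no scheduled reading before allocation, or was read late and unmasked.* The supplied text shows neither. It is silent on the reading, and the forms are missing.
- *That misreading alone could account for the gap between subgroups.* The documents give no subgroup sizes, no spread of displacement around 5 mm and no reading error, so such an effect cannot be sized. Reading error unrelated to arm and outcome would generally shrink the contrast.

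The defence does not supply the missing facts. A non-treating surgeon is not necessarily unaware of allocation, and a prospective assessment of severity is not a recorded measurement in millimetres. The protocol also still plans no displacement subgroup.

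**Conclusion.** The point holds as a gap in how subgroup membership was fixed, in a split that the protocol did not plan. It is not evidence of a biased reading. It does not touch the primary pain estimate. It bears on the claim that benefit is larger at 5 mm or more, where the SAP sets 2.2 against 0.9 points and 97% against 41%.

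The contrast itself supports caution. At about 1.3 points, with an approximate 95% interval of -0.25 to 2.85, a difference between subgroups is likely but not settled, even if every fracture was read correctly. That figure assumes independent, roughly normal posteriors. The judgement on measurement rests on the supplied text alone; a form field together with a concealed reading of admission films would answer that part.

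**What to change.** 1. In the protocol, add initial posterior displacement in millimetres to the injury characteristics list. Have the non-treating surgeon's existing review record it from admission images only, with allocation and outcome concealed.
2. Because the analysis is already done, state in the SAP the image, reader, date and concealment of the reading that was used. If it was not a concealed reading of admission images, re-read the stored admission films with treatment concealed and form the 5 mm subgroups from that reading.
3. Label the split post hoc and exploratory unless prespecification can be shown.
4. Report the between-subgroup contrast with its credible interval from the model, in place of the column of differences in probability.

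The cost is a few minutes per case, on a review already made for every fracture or in one pass through stored films, and a more cautious subgroup statement. If a suitable reading already exists, the measurement question closes with a sentence in the SAP.

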Our primary hypothesis is that the operative treatment group will have lower VAS pain scores compared to the non-operative treatment group both during their hospital stay and in the short-term outpatient follow-up.

Based on the results of a pilot study, we expect pain scores in the non-operative group to have a mean of 5.7 and a standard deviation of 2.3. Assuming a 20% reduction in pain scores, 130 patients (65 per arm) are required to have an 80% chance of detecting, as significant at the 5% level, a decrease in the primary outcome measure from 5.7 in the control group to 4.56 in the experimental group. This is our primary outcome and the study will be powered for this variable.

Primary data analysis will involve direct comparison of the change in value of the reported pain scores at the time points listed below. We will be powered to detect a 20% reduction in pain. Secondary analysis will compare the value of narcotics administered at the distinct time periods. Tertiary analysis will be comparing the time (in days) to mobilization with physical therapy. The previous retrospective pilot study incorporated a propensity factor, generated from well documented sources of pain. As this is a prospectively randomized trial, we do not anticipate needing to accommodate for matching.

RANDOMIZATION

Eligible patients will be randomized in equal proportions to one of the two treatment groups: 1) operative treatment of the lateral compression type fracture, 2) non-operative treatment of the lateral compression type fracture. Allocation will be concealed using a centralized 24-hour computerized randomization system, www.randomize.net, that will allow Internet based allocation. The treatment allocation will be stratified on the following prognostic factors to ensure balance between the intervention groups: 1) patient intubation status at time of enrollment, 2) patient prescription pain medication usage during the month prior to injury.

DATA MANAGEMENT

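### Effect modification by degree of displacement is examined only through one unexplained 5 mm cut, and robustness to that cut is not shown

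*SAP*

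**What the plan says.** The SAP's Statistical Analysis section states the aim and the method together: "To assess possible effect measure modification based on the initial degree of displacement, we stratified the sample to create two subgroups". The groups are 5 mm or more and less than 5 mm. The estimation step follows: "We then calculated the average effect of operative treatment on pain in each of the subgroups".

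The displacement table at the end of the SAP presents "The posterior probability of surgical fixation achieving a clinically significant reduction in mean BPI pain scores stratified by fracture displacement". It gives a mean difference of 2.2 points (95% credible interval 0.9 to 3.5) at 5 mm or more and 0.9 points (0.1 to 1.8) below 5 mm. It then lists posterior probabilities at five pain-reduction thresholds from 0 to 2.0, with a column of differences between those probabilities. What is varied is the size of the pain benefit: "Several possible clinically significant pain reduction thresholds are presented". The displacement cut is not varied.

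The protocol's Data Analysis section plans comparisons between treatment groups ("Primary data analysis will involve direct comparison of the change in value of the reported pain scores at the time points listed below") and no displacement subgroup. Displacement in millimetres is not among the injury characteristics under Assessment of Study Injuries, and displacement is not a stratification factor under Randomization. Apart from titles in the reference list, the visible protocol uses the word only under Potential Risks, for a later complication of non-operative care.

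**The concern.** The stated question is about degree, which is a continuous quantity. The analysis can answer only whether patients on either side of one line differ. It treats the effect of surgery as constant within each side and allows it to change only at 5 mm. No argument for that shape appears in the visible text.

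Two things follow. First, the reader cannot distinguish a benefit that rises steadily with displacement from one that jumps at a threshold, nor judge how much the reported contrast owes to where the line was put. The SAP is dated December 2020, is written in the past tense and contains results, so the documents do not show that 5 mm was fixed before the data were seen. Second, if the true relation is gradual, two groups estimate it less precisely than the measured values would. That matters because the contrast between the strata is already imprecise.

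**Working it through.** **1. Reproduce the SAP's table.** Inputs: the two means and credible intervals in the displacement table. Assuming roughly normal posteriors, SD = interval width / 3.92.

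- 5 mm or more: (3.5 - 0.9)/3.92 = 2.6/3.92 = 0.663
- Below 5 mm: (1.8 - 0.1)/3.92 = 1.7/3.92 = 0.434

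P(benefit > t) = 1 - Φ((t - mean)/SD):

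| Threshold t | ≥5 mm, table | ≥5 mm, computed | <5 mm, table | <5 mm, computed |
|---|---|---|---|---|
| 0 | >99% | 100.0% | 98% | 98.1% |
| 0.5 | 99% | 99.5% | 82% | 82.2% |
| 1.0 | 97% | 96.5% | 41% | 40.9% |
| 1.5 | 88% | 85.4% | 8% | 8.3% |
| 2.0 | 65% | 61.8% | 1% | 0.6% |

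The largest gaps, 2.6 and 3.2 points in the upper stratum, can be explained by rounding of the mean and the shape of the posterior. The table is internally consistent, and the normal approximation is adequate for what follows.

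**2. The contrast between strata, which the SAP does not report.** Treating the two posteriors as independent:

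- Difference = 2.2 - 0.9 = 1.3 points
- SD = √(0.663² + 0.434²) = 0.79
- Approximate 95% interval = 1.3 ± 1.96 × 0.79 = -0.25 to 2.85
- P(larger benefit at 5 mm or more) = Φ(1.3/0.79) ≈ 95% (93.5% to 96% allowing for rounding of the two means)

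**3. Share of patients at or above the cut.** The documents do not give it. With equal residual SD and the same operative/non-operative split in both strata, variance is inversely proportional to size. The variance ratio is (0.663/0.434)² = 2.34, so the share is 1/(1 + 2.34) ≈ 30%. Neither condition can be checked. Moving each interval width by 0.1 for rounding gives 26% to 34%. An 80/20 treatment split in the upper stratum against 50/50 in the lower gives 1/(1 + 2.34 × 0.16/0.25) ≈ 40%. I therefore use 20% to 50%.

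**4. Information kept by one cut, if benefit is linear in displacement.** The fraction kept is the squared correlation between displacement X and the indicator X > c. With share p above the cut:

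- Normal: φ(z)²/[p(1 - p)], where z is the 1 - p quantile
- Exponential: (p ln p)²/[p(1 - p)]
- Log-normal with log-SD s: [Φ(s - z) - p]²/[(exp(s²) - 1) p(1 - p)]

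| Distribution (assumed) | p = 20% | p = 30% | p = 50% |
|---|---|---|---|
| Normal | 0.49 | 0.58 | 0.64 |
| Exponential | 0.65 | 0.62 | 0.48 |
| Log-normal, s = 0.5 | 0.61 | 0.61 | 0.52 |
| Log-normal, s = 0.8 | 0.56 | 0.51 | 0.37 |

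For normal and exponential shapes the loss is 1 - 0.65 = 35% to 1 - 0.48 = 52%. The standard error of the modification is then 1/√0.65 = 1.24 to 1/√0.48 = 1.44 times what it need be. With the more skewed log-normal (s = 0.8) the loss runs from 44% to 63%.

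**5. What cannot be computed.** The effect at another cut, or the slope per millimetre, needs patient-level displacement, which the documents do not contain.

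**The case against.** The strongest reply is that the loss depends on linearity. The squared correlation is symmetric: if benefit really steps at about 5 mm, a linear term loses the same fraction that the cut loses under a linear truth. The documents favour neither shape, and a spline check spends precision that a subgroup analysis can ill afford. This stands. The percentages in the working are conditional, and the case for a continuous model is that it addresses the SAP's own question about degree, not that it is more efficient in every case.

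The scale of the issue is also limited. The SAP introduces this table among extra results left out of the main article and speaks only of possible modification, so it is supplementary. Reading it as the trial's leading clinical message has no basis in the documents. The SAP describes the analysed fractures as minimally displaced and gives no range, so widely displaced cases may be few.

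A rationale for 5 mm, or recording of displacement in millimetres, may exist in material not available here: the case report forms are an attachment, part of the protocol was removed, and the main article is not provided. The statement that no reason is given therefore applies to the visible text only.

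A reader might also infer that the finding is produced by the cut, would disappear at another one, or was chosen from the data. The documents show none of these. They show only that robustness to the cut is not reported.

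**Conclusion.** The point holds as a modest improvement to a supplementary analysis; the primary comparison is unaffected. A question about degree is answered with a single 5 mm split that the visible text does not justify, the visible protocol does not name and no sensitivity analysis tests.

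Under a roughly linear effect and 20% to 50% of patients at or above the cut, about 35% to 52% of the information on modification is lost for normal or exponential displacement. The loss is larger under strong skew and small if there is a true step near 5 mm. The effect shape, distribution and share are all assumptions.

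The approximate contrast has an interval that includes zero, so gaps of up to 80 percentage points in the table's difference column should not be read as the strength of evidence for modification.

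**What to change.** **If millimetre values are already recorded:** add one model in the SAP's existing Bayesian hierarchical framework, fitted to all patients, with treatment, displacement in mm and their product. Use a linear term, with a log or spline version to check the shape. Report the treatment effect across the observed range of displacement and the posterior for the interaction, each with a 95% credible interval. Keep the 5 mm table and label it descriptive.

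**If only the category was kept:** report the contrast between strata with its credible interval from the model itself (the approximation above is 1.3 points, -0.25 to 2.85), and state that dependence on the 5 mm cut could not be examined.

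**In either case:** state where 5 mm came from and when it was set.

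**Cost:** a few lines of SAP text and one more model in software already in use. The downside is a shape assumption, which the log or spline check tests only as far as the data allow. Re-reading stored films to recover millimetre values would need extra resources and is not part of this request.
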